Patient Aligned Care Team (PACT) Intensive Management (PIM) Project Protocol

Modified 1-29-2020

Contents

Background	2
Summary of outcome measures	2
Primary and Secondary Outcome Measures Procedures	4
Sample selection and recruitment	4
Demonstration Site Selection:	4
Inclusion criteria:	4
Exclusion criteria:	5
Sample	5
Interventions	6
Measurements	6
Analysis	6
Other Outcome Measures	7
Functional Status, Quality of life, Symptom Burden	7
Implementation Outcome/challenges	7
Sample selection/ recruitment	7
Instrument Development	8
Procedures	8
Analysis	8
Primary Care Staff Job Satisfaction and Intention to Stay at the VA	8
Sample	8
Method	8
Analysis	9

Background

In 2013, VHA Primary Care Services submitted a request for proposal (RFP) seeking VA Medical Center (VAMC) participation in a national PACT Intensive Management (PIM) initiative. The specific objectives of the initiative were to 1) reduce preventable hospitalizations and emergency care in persons having complex medical and social needs and who are identified as being at highest risk for unplanned visits, hospitalization, and death, 2) optimize high-risk patient functional status, and 3) maintain high-risk patients in their homes and communities to the greatest extent possible. Through the RFP, five VAMCs were selected to receive funding for up to \$750,000 per year to support demonstration projects to innovate strategies to manage high-risk Veterans in a rigorously evaluated quality improvement project. Through this initiative, the PIM teams at each of the demonstration sites became subject matter experts and valuable advocates for high-risk patients' individual and system-level needs.

Summary of outcome measures

Primary Outcome Measure:

1. VA health care cost
Total costs of VA care, including inpatient, outpatient, pharmacy and fee-basis services.

Secondary Outcome Measures:

2. Healthcare Utilization

VA central repository administrative data will be analyzed to calculate utilization of hospital, emergency and outpatient primary and specialty care. This information will be electronically abstracted through the VA central repository administrative data center.

3. Medicare utilization and cost

Medicare claims data was used to capture utilization and costs for services reimbursed by Medicare. The Master Beneficiary Summary File was used to ascertain patients' Medicare enrollment status.

Other Pre-Specified Outcome Measures:

4. Engagement

The investigators will look at patient PIM enrollment data by utilizing central repository administrative data. The data will be electronically abstracted through the VA central repository administrative data center.

5. Functional status

Patient report of their physical, social, and mental functional status is routinely collected as part of their medical visit. The data will be abstracted through the VA central repository administrative data.

6. Quality of Life Status

Patient assessment of their quality of life collected as part of their medical care. This information will be electronically abstracted through the VA central repository administrative data center.

7. Symptom Burden

Patient assessment of mental health and physical health symptom burden is routinely collected as part of their care and documented in their medical record. This data will be electronically abstracted through the VA central repository administrative data center.

8. Implementation Outcome/ challenges

Information about implementation barriers and facilitators, feasibility, and sustainability will be obtained through two waves of key stakeholder interviews, including demonstration site staff and facility leaders

9. Primary Care Staff Job Satisfaction and Intention to Stay at the VA

The investigators will survey Primary Care Providers (PCPs) (physicians, MDs/DOs; nurse practitioners, NPs; physician assistants, PAs) and nurses (registered nurses, RNs; licensed practical nurses, LPNs; licensed vocational nurses-LVNs) at the five healthcare systems that have a PIM team. They will use both online using RedCap and paper-and-pencil versions of the survey to increase response rate. The investigators will survey Primary Care staff at baseline and one year later. The first survey was fielded December 2014 - May 2015 and again from October 2016 - January 2017). Primary Care Staff Job Satisfaction is measured by a single item "Overall, I am satisfied with my job," rated on a 5-point Likert agreement scale.

10. Primary Care Staff Intention to Stay at the VA

The investigators will survey Primary Care Providers (PCPs) (physicians, MDs/DOs; nurse practitioners, NPs; physician assistants, PAs) and nurses (registered nurses, RNs; licensed practical nurses, LPNs; licensed vocational nurses-LVNs) at the five healthcare systems that have a PIM team. They will use both online using RedCap and paper-and-pencil versions of the survey to increase response rate. The investigators will survey Primary Care staff at baseline and one year later. The first survey was fielded December 2014 - May 2015 and again from October 2016 - January 2017). Intention to Stay at the VA is measured by a single item "I intend to continue working in PC at the VA for the next two years," rated on a 5-point Likert agreement scale.

Primary and Secondary Outcome Measures Procedures

Sample selection and recruitment

Demonstration Site Selection: Five sites will be selected in a competitive process by reviewers and funders from the VHA Office of Primary Care Services. Selection criteria include sites that: 1) have geographically diverse teams, spanning both rural and urban settings; 2) have teams that include a mental health provider; and 3) provide services that can increase Veteran access to healthcare, including home visits and telehealth.

Inclusion criteria: The evaluation team will collaborate with demonstration sites over six months to define and identify the high-risk Veteran population using the CAN score (Wang et al.) The CAN score is computed weekly for each VHA patient based on multiple electronic data elements (i.e., clinical diagnoses, laboratory data, vital signs, previous inpatient and outpatient utilization over the preceding year) and predicts risk of hospitalization in the subsequent 90 days. The patient lists will include those on the top 10th percentile of the CAN score and that had at least one ED visit or hospitalization in the VHA over the prior 6 months. All patients will have an assigned primary care medical homes in general Primary Care, Women's Health, Geriatrics, or Infectious Disease (mostly caring for patients with Human Immunodeficiency Virus, HIV). The Infectious Disease medical home will be included as a tracer for assessing specialty medical homes, to provide formative information on differences from primary care medical homes.

Table 1. Exclusion Criteria

Exclusion Criteria

• A clinical encounter with specialty primary care teams with comprehensive resources other than those identified in inclusion criteria (i.e., Post-Deployment, Renal, Spinal

Cord Injury, Homeless PACT, Home-Based Primary Care team), in the previous two months

- Outpatient encounters in Mental Health Intensive Care Management programs (VHA-adapted Assertive Community Treatment program), palliative care, and hospice in the previous two months
- Nursing home in the previous two months
- Care Assessment Need Score (CAN) (Wang et al.) < 90th percentile
- Inpatient admission to a residential substance abuse treatment program in the previous two months
- Death

Exclusion criteria: Patients will be excluded if they are managed by an intensive primary care team or have received intensive outpatient services in the past two months, such as homeless primary care services, primary care for home-bound patients, intensive outpatient mental health services. Patients residing in a VHA nursing home facility or residential substance abuse treatment program in the previous two months will also be excluded. Full exclusion criteria are listed in Table 1.

Sample: The evaluation team will randomly identify a sample of high-risk Veterans from among patients assigned to a primary care medical home at a demonstration site. Half of these patients will be randomly allocated to the innovation group and sent to the demonstration teams for recruitment consideration, and the other half will be allocated to usual care in the VA patient-centered medical home. The investigators will stratify by gender to ensure representation of 10% women in both the innovation group and the usual care group to inform future policy. Demonstration teams will receive lists of high-risk patients from the evaluation team through a secure workspace behind VHA firewall. Demonstration patients on this list are considered innovation patients (intent-to-treat), if they receive services from the demonstration teams. Demonstration teams will be blinded to the list of usual care patients in the comparison group as part of the quality improvement design.

Local healthcare providers will be permitted to refer a limited number of Veterans to the intensive primary care programs (up to 10% of the program capacity). To allow usual care patients the opportunity to participate as a demonstration patient, after 12 months, high-risk Veterans in the usual care group will not be excluded from being randomly selected for an invitation to participate in the intensive management innovation.

Based on a univariate comparison, a sample size of 526 patients per evaluation arm (1052 total) will provide 90% power to detect a small effect (Cohen's $d = 0.2$) in ED visits or hospitalizations with a two-sided significance level of 0.05. The investigators estimate that at least 200 patients will have the opportunity to be invited to the intensive management program at each demonstration site over a one-year period, which will provide a sufficient sample size of 1000 patients in the innovation and 1000 in the comparison arm. Sites control the frequency and

quantity of high-risk patients identified to them each month, based on clinical and resource considerations. PIM teams are expected, however, to receive at least 200 names over 12 months, rather than all 200 at the beginning.

Interventions

Selected demonstration sites will span a variety of high-risk patient care approaches, such as a patient-centered medical home for high-risk Veterans, collaborative care model for high-risk patients, and care transitions program. Each site will propose a site-specific intervention. All proposed interventions will use population management models and determine their own approaches to stratifying patients and determining eligibility for and intensity of services. The types of services offered by each team will depend on program staff, local resources, and facility and program priorities. Each site will also develop its own criteria for when to discontinue services for patients.

Measurements

Patient demographics, chronic conditions and other health conditions (Yoon, Scott, Phibbs, & Wagner, 2011), comorbidity score (Charlson), VHA outpatient/inpatient utilization, measures of prescription drug use and mortality will be obtained through the VHA Corporate Data Warehouse. For costs, VHA inpatient and outpatient utilization records will be linked to Managerial Cost Accounting (MCA) cost data to obtain the costs of outpatient and inpatient care. Pharmacy utilization and costs will be obtained from MCA Pharmacy files, and VHA-sponsored care is obtained from Fee Basis files. Implementation costs will be determined through micro-costing methods from site reports. Because these are administrative data, these are collected from each participant regardless if they were not offered services or if they were discontinued from the intervention.

Analysis

The investigators will conduct an intent-to-treat analysis based on patients' allocated group. The investigators plan to compare unadjusted mean utilization counts and costs for different categories of inpatient care and outpatient care and total care. The investigators will estimate the impact of PIM using regression models to obtain the differences-in-differences estimate of the change from the 12-month pre-intervention period to 12-month and 24-month post-intervention period attributable to PIM above and beyond any time trends that occurred in both groups. Our regression models will predict utilization of outpatient encounters and inpatients stays in count data models (Poisson and negative binomial regression models) including a time-varying measure of risk using the Charlson Index and patient fixed effects to account for factors fixed over time. Regression models of costs include the same predictors as the utilization models and will be conducted using ordinary least squares (OLS); sensitivity analyses will be conducted using generalized linear models (GLM) with a log link and Poisson distribution. Mortality will be compared between treatment groups with a log-rank test for equality of survivor functions.

In other sensitivity analyses, the investigators plan to conduct regression models with patient random effects and covariates for patients' age, gender, race/ethnicity, marital status, means test, service connection, homelessness, Charlson Index, and site. The investigators will also measure the treatment effect on the treated by conducting regression analysis using instrumental variables to examine whether more PIM encounters were related to cost and utilization impacts by using randomization to PIM as an instrument for number of PIM encounters. Instrumental Variable models will use the two-staged least squares estimator.

Other Outcome Measures

Functional Status, Quality of life, Symptom Burden

Standardized assessments of symptom burden (mental health and physical health), quality of life, and functional status (physical, social, and mental) will be based on patient-reported outcomes measurement information system (PROMIS) global items. These measures will be obtained only on the innovation patients and entered into the electronic medical record using a standardized assessment template available only to the demonstration staff. Some standardized assessments are available on the entire sample as part of VHA medical records (i.e., pain score, Patient Health Questionnaire (PHQ)-2 for depression) and performance measures.

Implementation Outcome/challenges

Sample selection/ recruitment

The investigators will interview PIM staff about implementation challenges and lessons. The investigators will use PIM staffing lists from the demonstration sites to compile the sampling frame. The investigators will include in the sampling frame the team leaders, team members, and program coordinators. The investigators will select all PIM team leads and program coordinators (if the site has a coordinator), and randomly select 1 of each job title/role from the PIM team members. Team members who refuse or are ineligible will be replaced by randomly selecting another person in the same job title/role, until one completed interview is obtained for each job title/role for each site. Team members will include RNs, NPs, MDs, social workers, psychologists, and intermediate care technicians. The investigators will invite 35 potential respondents by email, and follow up by telephone and using instant messaging for those who do not respond to the initial email.

With approval from site and program leadership, stakeholders will be sent an email describing the interviews and inviting them to participate. If stakeholders do not respond to the invitation email within 2-3 business days, the investigators will follow up by either phone, instant message, or additional emails. Methods of communication will be determined by available contact information and perceived individual stakeholder preferences. The investigators will make 3 follow-up contact attempts.

Instrument Development

Two qualitative team members drew on the Consolidated Framework for Implementation Research (CFIR) and chronic care model to develop the interview guides. The interviews are designed to take approximately 30 minutes, except the program lead interviews which are approximately 60 minutes. Interview guides will be refined through piloting and consultation with PIM and evaluation team clinicians.

Procedures

Interviews will be conducted by telephone. The investigators will analyze the transcripts of these interviews thematically, guided by the Consolidated Framework for Implementation Research and the Chronic Care Model.

Analysis

All interviews will be audio recorded. Audio recordings of the interviews will be transcribed in full. Summaries will be created from the transcripts, or directly from the audio recordings, using standardized templates based on the interview guides, with additional sections included for recording good quotes, emergent themes, and analyst observations. The summarized data will then be organized into Excel matrices to facilitate within and across site comparisons.

The substantive findings from these comparisons will be disseminated to the evaluation team, the PIM sites, and to VA central office via Powerpoint presentations and written reports, providing a richly detailed record of stakeholders' perceptions of the PIM pilot project and PIM program activities and providing timely and specific formative feedback that will be used to shape and improve PIM.

[Primary Care Staff Job Satisfaction and Intention to Stay at the VA.](#)

Sample

The investigators will survey all Primary Care Providers (PCPs) (physicians, MDs/DOs; nurse practitioners, NPs; physician assistants, PAs) and nurses (registered nurses, RNs; licensed practical nurses, LPNs; licensed vocational nurses-LVNs) at the five healthcare systems that have a PIM team.

Method

The investigators will use both online using RedCap and paper-and-pen versions of the survey to increase response rate. The investigators will survey Primary Care staff at baseline and one year later. The first survey will be fielded December 2014 - May 2015 and again from October 2016 - January 2017).

Analysis

Longitudinal cohort of staff who responds to both Wave 1 and Wave 2. The investigators will use ordinary least squares regression analysis to examine associations between the independent variable measured at wave 1 and outcome variables measured at wave 2 controlling for wave 1 outcomes among staff who completed both waves. The investigators will focus on Job Satisfaction and Intention to Stay at VA as dependent variables. The investigator will adjust for provider-level covariates (type of staff, location, type of primary care team, gender, length of time at VA) and clustering of respondents within clinics assuming a random effect using robust standard errors. The investigators will use sample weighting for nonresponse based on provider characteristics in both waves and conduct multiple imputations for item-level missing data;

Difference-in-differences between Wave 1 and Wave 2: will treat Wave 1 and Wave 2 as two independent samples and use difference-in-difference regression analysis to assess differences in outcome variables between Wave 1 and Wave 2 among PIM and usual care. The investigators will focus on primary care staff experience (e.g., stress, satisfaction with help received) working with high-risk patients as dependent variables. The investigators will adjust for covariates (type of staff, location, type of primary care team, gender, length of time at VA). The investigators will use sample weighting for nonresponse based on provider characteristics in both waves.

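### The Sample paragraph ties the intent-to-treat label to receiving services, against the protocol's own random allocation and its analysis by allocated group

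*Protocol*

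**What the plan says.** Under Sample selection and recruitment, the Sample paragraph first describes random allocation: "Half of these patients will be randomly allocated to the innovation group and sent to the demonstration teams for recruitment consideration", with the other half going to usual care. A few sentences later it says who counts: "Demonstration patients on this list are considered innovation patients (intent-to-treat), if they receive services from the demonstration teams".

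Other parts of the protocol bear on the same question:

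- **Analysis** (primary and secondary outcomes): "The investigators will conduct an intent-to-treat analysis based on" the patient's allocated group.
- **Measurements**: the administrative data cover everyone; "these are collected from each participant regardless if they were not offered services or if they were discontinued from the intervention".
- **Sample, sample-size text**: the 1000 innovation patients are counted on the basis that "at least 200 patients will have the opportunity to be invited to the intensive management program" at each site.
- **Sample, referrals**: local providers are "permitted to refer a limited number of Veterans to the intensive primary care programs (up to 10% of the program capacity"), so the teams will also serve some patients who were never randomised.
- **Interventions**: the sites "determine their own approaches to stratifying patients and determining eligibility for and intensity of services".
- **Analysis, sensitivity analyses**: the effect of treatment received is estimated separately, "using randomization to PIM as an instrument for number of PIM encounters".

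The section on functional status, quality of life and symptom burden restricts the PROMIS measures to innovation patients and has them recorded through a template that only demonstration staff can open. There the term appears to mean patients who were served.

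**The concern.** Intent-to-treat membership is fixed at randomisation. Receipt of services is decided afterwards, by the site team's view of eligibility and by the patient's acceptance, and nothing in the usual-care arm corresponds to it. The Sample sentence therefore puts the label on a group that leaves out patients who were allocated but not served, while the Analysis section includes them.

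If the analysis set or the participant flow were taken from the Sample sentence, a selected innovation arm would face an unselected usual-care arm. Three analyses would be affected differently:

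- **Unadjusted mean costs and utilisation**: biased by any difference in level between served and unserved patients.
- **Log-rank mortality comparison**: biased because a patient must survive to be served.
- **Fixed-effects difference-in-differences models**: biased only so far as served patients differ in their change over time.

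The wording also leaves the innovation group (allocated) and innovation patients (apparently served) undistinguished, although later sections rely on the difference.

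**Working it through.** **1. The passages side by side.** Allocation precedes any contact, since allocated patients are sent to the teams for consideration. The analysis is by allocated group. Outcome data are collected even where services were not offered. The arm size counts patients who could be invited. Using randomisation as an instrument for the number of encounters needs the allocated patients with zero encounters. Only the Sample sentence makes membership depend on service.

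**2. The protocol's own figure.** For d = 0.2, two-sided 0.05 and 90% power, n per arm = 2(1.960 + 1.282)²/0.2² = 525.4, so 526. It reproduces and is not in dispute. The planned arm is 5 × 200 = 1000.

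**3. Effect on sample size.** With uptake e, the Sample sentence gives 1000e innovation patients. This falls below 526 when e is under 526/1000 = 52.6%. Against 1000 usual-care patients, the precision of 526 v 526 is kept with 1/(2/526 − 1/1000) = 356.9, so 357 served. The problem is selection rather than power.

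**4. Illustration of the bias.** The protocol gives no uptake, so every input here is assumed, and the true effect is set to zero. Let served patients exceed unserved ones by δ = 0.2 SD.

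- Unadjusted means: bias = (1 − e)δ.
- Difference-in-differences on an additive scale, as in the OLS cost model, with δ the pre-period gap and a share ρ = 0.5 persisting: bias = −(1 − e)(1 − ρ)δ. If the gap is stable (ρ = 1), the bias is 0.
- Type I error of the unadjusted comparison: standard error √(1/1000 + 1/(1000e)), nominal level 0.05.

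| Uptake e | Unadjusted bias (SD) | Difference-in-differences bias (SD) | Type I error, unadjusted |
|---|---|---|---|
| 90% | 0.1 × 0.2 = 0.02 | −0.01 | about 0.07 |
| 50% | 0.5 × 0.2 = 0.10 | −0.05 | about 0.45 |
| 30% | 0.7 × 0.2 = 0.14 | −0.07 | about 0.57 |

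**5. Mortality at 24 months.** Assume a constant hazard, annual mortality m and first service t = 1 to 3 months after allocation. Usual care: 1 − (1 − m)². Served-only, counted from allocation: 1 − (1 − m)^(2 − t/12).

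| m per year | Usual care | Served-only, t = 1 to 3 months |
|---|---|---|
| 5% | 9.8% | 9.4% to 8.6% |
| 10% | 19.0% | 18.3% to 16.8% |
| 15% | 27.8% | 26.8% to 24.8% |

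The gap arises with no effect on survival.

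**The case against.** The strongest reply is that the analysis is already settled. The sentence sits in the recruitment text, the Analysis section states the rule plainly, and the sample-size, measurement and instrumental-variable text all agree with it. Harm requires an analyst to prefer one recruitment sentence over all of these, so it may be no more than a drafting slip. This stands as a limit on the likely practical impact. It does not remove the contradiction, which lies in the paragraph a reader consults to learn who belongs to the arm.

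A second reply is that the sentence says *if*, not *only if*, and may have been meant to separate listed patients from provider-referred ones, or to name those served. Either intention is possible. But a condition in a definition is naturally read as a requirement, and on both readings the label omits patients who were allocated but not served.

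Third, the illustrations rest on assumed inputs, and the additive difference-in-differences formula suits the OLS cost model better than the Poisson and negative binomial utilisation models. In those, a stable additive gap combined with a common time trend need not cancel. Both points are right: the figures show direction and rough scale, and are not estimates for this trial.

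Finally, the rule for re-drawn usual-care patients could be seen as a separate matter. It already follows from analysis by allocated group, and belongs in the same clarification.

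**Conclusion.** The concern holds. The protocol describes its intent-to-treat group in two incompatible ways, and the one in the Sample paragraph is wrong as written. That conclusion rests on the text and needs no calculation. No bias arises if the Analysis section is followed. If the Sample sentence were followed, the unadjusted means and the log-rank test would be exposed to selection, and the difference-in-differences estimates to the extent that served patients change differently over time. The actual size cannot be computed without uptake and the served-unserved difference. This should be fixed, but it does not undermine the planned primary analysis.

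**What to change.** Replace the Sample sentence with wording such as: *All patients randomly allocated to the innovation list are innovation patients for the intent-to-treat analysis, whether or not they are contacted, judged eligible by the team, enrolled or served; provider-referred patients who were not randomised are not included.* Add that a usual-care patient drawn for invitation after 12 months stays in the first allocated group for this analysis.

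Use a separate term, for example *served innovation patients*, for the engagement outcome, for the PROMIS measures recorded by demonstration staff, and for describing treatment received in the instrumental-variable analysis, which itself keeps all randomised patients.

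The cost is a rewording in the Sample paragraph and a matching term in the later sections. The administrative outcomes already cover every allocated patient, and the 526 per arm does not change. The PROMIS measures still describe served patients; their population is simply named.

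The estimate may look smaller than in a served-only comparison. If 0.2 SD acted only in those served, the intent-to-treat effect would be 0.2e. At 50% uptake that is 0.10 SD, with about 61% power at 1000 per arm. The effect detectable with 90% power at 1000 per arm is 3.242 × √(2/1000) = 0.145 SD, so about 0.145/0.2 = 72.5% uptake would be needed. This dilution already follows from the Analysis section and is not caused by the rewording.

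### Patients are randomised, yet the primary cost outcome is analysed by patient fixed-effects difference-in-differences; adjusting for pre-period cost would probably give a narrower interval from data already held

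*Protocol*

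**What the plan says.** Under Summary of outcome measures, the single primary outcome is VA health care cost: "Total costs of VA care, including inpatient, outpatient, pharmacy and fee-basis services".

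The Sample section sets up a concurrent randomised comparison: "Half of these patients will be randomly allocated to the innovation group", with the other half in usual care. The Analysis section, under Primary and Secondary Outcome Measures Procedures, analyses patients by allocated group.

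That section obtains the effect by "using regression models to obtain the differences-in-differences estimate of the change from the 12-month pre-intervention period" to 12 and 24 months afterwards. It gives two reasons. One is to isolate the change "attributable to PIM above and beyond any time trends that occurred in both groups". The other lies in the model, described as "including a time-varying measure of risk using the Charlson Index and patient fixed effects to account for factors fixed over time". Cost is tied to the same specification: "Regression models of costs include the same predictors as the utilization models and will be conducted using ordinary least squares (OLS".

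The other cost analyses are a plan to "compare unadjusted mean utilization counts and costs", a log-link GLM, "regression models with patient random effects and covariates", and an instrumental-variable model. None of them names pre-period cost as a covariate.

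**The concern.** Difference-in-differences (DiD) with unit fixed effects is a tool for non-randomised comparisons. Here, concurrent random allocation already balances common time trends and fixed patient factors in expectation, so neither stated reason requires it. Its price is that pre-period cost enters with a slope fixed at 1.

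The true slope is probably below 1. The Inclusion criteria select patients in the top tenth of CAN scores who had an ED visit or admission in the prior 6 months, which falls inside the 12-month pre-period. Some regression to the mean is therefore likely. This is an inference; the protocol reports no slope or correlation.

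At stake is the width of the interval for the only primary outcome, and so how large a saving or added cost the trial can rule out. The sample size was set for ED visits or hospitalizations, and the protocol states no precision target for cost.

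**Working it through.** **The plan's own figure.** For d = 0.2, two-sided 0.05 and 90% power, n per arm = 2 × (1.960 + 1.2816)² / 0.2² = 525.4, so 526. The stated figure reproduces. It is a univariate calculation for ED visits or hospitalizations, so it does not settle precision for cost. The expected 1000 per arm (Sample section) is used below.

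**Inputs not in the protocol, all assumed.** rho = pre-post correlation of cost; k = pre-period SD / post-period SD; s = share of cost variance explained by Charlson; rc = pre-post correlation of Charlson.

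**What the planned model is.** With one pre and one post period, fixed effects amount to regressing (post cost − pre cost) on arm and on (post Charlson − pre Charlson). Equivalently, post cost is regressed on arm with the pre-cost coefficient fixed at 1 and the pre-Charlson coefficient fixed at minus the post-Charlson one. Freeing these constraints cannot raise the large-sample residual variance.

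**No covariates** (variances relative to post-period variance):
- DiD: 1 + k² − 2·rho·k
- Adjusted for pre-period cost: 1 − rho²
- Difference: (k − rho)², never negative, and zero only when k = rho, that is, when the post-on-pre slope is 1.

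With k = 1 the saving is (1 − rho)/2. The effect detectable with 90% power is (1.960 + 1.2816) × √(2f/1000), where f is the variance factor.

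| rho | DiD | Adjusted | Variance saved | Width saved | Detectable, DiD (SD) | Detectable, adjusted (SD) |
|---|---|---|---|---|---|---|
| 0.2 | 1.60 | 0.96 | 40% | 23% | 0.183 | 0.142 |
| 0.3 | 1.40 | 0.91 | 35% | 19% | 0.172 | 0.138 |
| 0.4 | 1.20 | 0.84 | 30% | 16% | 0.159 | 0.133 |
| 0.5 | 1.00 | 0.75 | 25% | 13% | 0.145 | 0.126 |
| 0.7 | 0.60 | 0.51 | 15% | 8% | 0.112 | 0.104 |

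Below rho = 0.5 the DiD factor exceeds 1, so DiD is then less precise than ignoring pre-period cost altogether.

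Other cases, for the same five values of rho:
- k = 0.8: 27/22/16/11/2% of variance saved.
- k = 1.25: 53/50/46/43/37%.
- Two post years pooled under compound symmetry, k = 1: 53/47/40/33/20%.

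**With Charlson** (k = 1, rho now for the cost not explained by Charlson):
- Planned model: 2(1 − rho)(1 − s)
- Adjusted, same Charlson terms: (1 − s)(1 − rho²), so again a saving of (1 − rho)/2
- Adjusted, baseline Charlson only: (1 − s)(1 − rho²) + s(1 − rc²)

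Saving of the baseline-Charlson model against the exact planned model, rc = 0.7:

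| s | rho 0.2 | 0.3 | 0.4 | 0.5 | 0.7 |
|---|---|---|---|---|---|
| 10% | 36% | 31% | 25% | 19% | 6% |
| 20% | 32% | 26% | 19% | 12% | −6% |
| 30% | 26% | 19% | 12% | 3% | −21% |
| Break-even s | 56% | 49% | 41% | 33% | 15% |

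Break-even s = (1 − rho)² / ((1 − rho)² + 1 − rc²); at rho 0.5 this is 0.25/0.76 = 33%. At rho 0.2/0.5/0.7 it is 46/25/11% for rc = 0.5 and 77/57/32% for rc = 0.9. At k = 0.8 and s = 10% the savings are 23/17/10/4/−9%.

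**Simulation** (1000 per arm, 2000 trials, rho 0.5, rc 0.7). Standard errors for planned / baseline Charlson only / same Charlson terms were 0.0442/0.0396/0.0387 at s = 10% and 0.0442/0.0436/0.0386 at s = 30%. The baseline-Charlson savings are 1 − (0.0396/0.0442)² = 20% and 1 − (0.0436/0.0442)² = 3%, against 19% and 3% from the formula.

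**Skewed costs** (lognormal, Charlson share about 0.06 to 0.11). The baseline-Charlson model saved 36/22/13/−2% at CV 1 (observed correlations 0.28/0.44/0.62/0.78) and 37/33/25/12% at CV 2 (0.21/0.35/0.53/0.71). Its robust 95% intervals covered 94–95%.

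**The case against.** **The planned estimator is valid and prespecified.** True. By the figures above it detects 0.112 to 0.183 SD at 1000 per arm, all below the d = 0.2 the protocol calls small. But that d was set for another outcome, and a narrower interval for the primary one costs nothing to collect.

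**The size of the gain is assumed.** This stands. None of rho, k, s or rc is in the protocol, and the computed savings run from 53% to −21%.

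**The practical alternative does not dominate the plan.** This also stands. A model with baseline Charlson only can lose when Charlson explains much of cost and rho is high. The planned model's advantage there comes from a Charlson value measured after allocation, which PIM could itself affect. If PIM does affect it, even the same-covariate comparison can reverse slightly: one simulation with a slope of 1 gave a DiD/adjusted variance ratio of 0.95.

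**Provider referrals could make fixed effects safer.** Suppose 10% of the arm were referred patients with stable costs 0.5 SD higher (assumed). The imbalance is 0.05 SD. At rho 0.5 and k = 1, adjustment keeps 0.025 SD of it, giving an RMSE of √(0.0387² + 0.025²) = 0.046 against 0.045 for DiD. The advantage would vanish. But the Analysis section analyses by allocated group, which keeps referrals out.

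**The random-effects sensitivity model may already cover this.** It depends on terms the protocol does not state. At rho 0.5, a common pre-period mean gives SE 0.0387, equal to adjustment; arm, period and arm-by-period terms give 0.0447, equal to DiD. Leaving those terms to an analysis plan is no fault, but the protocol does not secure a baseline-adjusted estimate.

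**Conclusion.** The concern holds. The protocol fixes, for its only primary outcome, an estimator that under randomisation is at best as precise as adjustment for pre-period cost. The conditions are large samples, the same other covariates, and a Charlson Index that PIM does not change. With equal pre and post SDs, the avoidable variance is 15% to 40% for correlations from 0.7 down to 0.2. Against the exact planned model, adjustment with baseline Charlson only is usually, but not always, more precise over the ranges examined.

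This is a loss of interval width. It is not bias, and it is not a failure to reach the stated power. The change should be made; confidence in the size of the gain is medium because every driving quantity is assumed.

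**What to change.** Make the primary cost model a regression of 12-month post-allocation total VA cost on allocated arm, 12-month pre-allocation total VA cost, baseline Charlson Index, site and gender, with robust standard errors. Use the same form at 24 months. Keep the fixed-effects DiD as a sensitivity analysis. If the random-effects model is specified further, a common pre-period mean (no arm main effect) would make it consistent with the adjusted model.

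The protocol is dated January 2020 and describes the Medicare data in the past tense, so results may be known. If arm-level results have been seen, keep the planned headline model and report the adjusted one as a labelled additional analysis, so that the change does not look data-driven.

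The cost is a few sentences of wording, with no new data or patients. The downsides are that the headline model is no longer DiD, and that precision could fall if Charlson explains more of cost than the break-even shares shown.
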